5.2 Safety Evaluation

Subject safety will be monitored by adverse events, vital signs, physical examinations, and laboratory data by the medical and study team as well as the independent safety monitoring committee.

Clinicians responsible for the care of study subjects receiving the NAVA mode of ventilation will be trained up to the current standard for their role, as is done for clinicians using clinically deployed ventilators (as listed in section 8.4.2). Guidelines for startup and continued management, including troubleshooting techniques, of NAVA mode will be available for the medical teams and a study investigator will round with the clinical team daily to provide expertise on the device/mode as well as be on call for assistance 24/7. Individual subjects will be withdrawn from the study for safety if an absolute increase in FiO_2 by 20% or if the $\text{pCO}_2/\text{TcO}_2$ increase by 25 points or greater than 90 mm Hg, which ever is achieved first, for more than 2 hours from baseline while on NAVA mode, The NAVA arm of the study will be discontinued and the patient will be transitioned to previous CMV settings. Study investigators will be available 24 hours day when a patient is on the trial.

The overall safety of the study will be assessed with interim safety analysis after the completion of every 5 patients (3 times total) and upon any serious safety events occurring.

6 STATISTICAL CONSIDERATIONS

6.1 Primary Outcome

The mean daily oxygen saturation index ($[\text{mean airway pressure} \times \text{FiO}_2]/\text{SpO}_2$) compared between NAVA and conventional mechanical ventilation will be the primary study outcome. Oxygen saturation index is a reliable surrogate measure for oxygenation index in children with moderate to severe lung disease that is used clinically and in research when arterial blood gas PaO_2 levels are not routinely available.

6.2 Secondary Outcome

The following secondary study outcomes will be compared between NAVA and conventional mechanical ventilation treatment periods. All outcome measures will be taken

from nursing and respiratory therapy charting in the EPIC or downloaded directly from the machines.

Measures of cardiorespiratory mechanics and stability:

- (1) Measures of respiratory mechanics: hourly mean PIP, MAP, tidal volume, respiratory rate, FiO₂, Edi (peak and min), and NAVA level. The NAVA catheter will be in place for the entire study (24 hour baseline and both crossover groups) for a consistent Edi measurement for both treatment arms and all over measures are comparable across machines and modes of ventilation.
- (2) The daily number of intermittent ($\text{SpO}_2 < 80\%$ for ≥ 10 seconds and less than 3 minutes) and prolonged ($\text{SpO}_2 < 80\%$ for ≥ 60 seconds) hypoxemic events recorded by continuous pulse oximetry.
- (3) Median hourly transcutaneous pCO₂ levels
- (4) Median daily Q4-6 hour OSI
- (5) Dynamic lung compliance.

Patient Comfort and sedation exposure:

- (1) Median daily State Behavioral Scale (SBS) and Withdrawal Assessment Tool (WAT-1) scores. Both scoring systems are validated measures of subject comfort and sedation requirements used in the CHOP intensive care units.
- (2) Daily frequency and total daily dose (mg/kg) of sedation medications.
- (3) Mean daily asynchrony index calculated as the number of asynchrony events divided by the sum of the ventilator cycles and ineffective efforts.
- (4) Salivary cortisol will be collected three times per day and averaged by the respiratory therapist. The daily average will be assessed and compared as a marker for patient stress on the different ventilator modes.

Long Term Outcomes

- (1) Postmenstrual age at discharge
- (2) Respiratory support required at discharge

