Study Phase	Screening	Unblinded Intervention			
		Observation Phase	1st Mode Phase	2nd Mode Phase	Observation
Study Days		1	2-6	7-11	12-discharge
Informed Consent	X				
Review Inclusion/Exclusion Criteria	X				
Demographics/Medical History	X				X
Vital Signs	X	X	X	X	
Ventilator settings/measurements/OSI	X	X	X	X	
Placement of Tcom (if applicable)		X			
Placement of NAVA catheter		X		X	
Randomization		X			
Daily Asynchrony Index		X	X	X	
Daily Salivary Cortisol Levels		X	X	X	
Adverse Event Assessment		X	X	X	X*

*We will monitor for targeted adverse events that may be related to the study procedures for 72 hours after completion of the 2nd mode phase.

FIGURE 1: STUDY DIAGRAM

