3.1.2 Study Observation Phase

Prior to beginning the initial treatment phase, all subjects will undergo a 24-hour period of observation with an Edi catheter in place while receiving CMV as ordered by the primary medical team. This period will be used to establish baseline Edi (Edi peak and Edi min), positive inspiratory pressure (PIP), and transcutaneous pCO₂ levels that will be employed in the study treatment phase.

At the end of the 11-day treatment phase, a second observation phase will begin and will be limited to medical record review. This phase will continue until the child is discharged in order to ascertain age and respiratory support needs at discharge.

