4.2 Unblinded Ventilator Mode Crossover Phase

Observation phase and Ventilation Mode crossover phases will have the same study procedures performed on a daily basis or less frequently as indicated.

- Placement of NAVA catheter. Catheter will be placed prior to the baseline monitoring phase and will be replaced before going into the 2nd ventilator mode on day 7 of the study.
- Placement of transcutaneous CO₂ monitor (Tcom) (if not already in use) will occur prior to the monitoring phase and remain throughout the 11 days of data collection.
- Salivary cortisol samples will be collected three times per day using a swab placed in the patient's mouth to collect pooled saliva. Samples will be collected at the same time each day and independently analyzed for cortisol values. The 3 cortisol values will be averaged for the 24 hour time frame.
- Asynchrony index will be calculated as the number of asynchrony events divided by the sum of the ventilator cycles and ineffective efforts for 1 minute. This will be determined two ways: first by physical assessment by the respiratory therapist with their patient/ventilator assessments every four hours and second by assessment of time delay or complete miss of neural trigger compared to ventilator trigger from ventilator waveforms.
- Download of data from the ventilators and clinical monitoring equipment as well as extraction of information from the electronic medical record will be done for data normally documented as part of routine clinical care.

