5.1.5 Ventilatory Parameters

The following parameters will be collected and trended from the ventilator:

- FiO₂
- RR

- Vt
- MAP
- PIP
- PEEP
- Dynamic Lung Compliance (Crs)
- Dynamic Lung Resistance (Rrs)
- NAVA level
- Edi peak and min - measured from the Edi Catheter that will remain in place during the 11 days of data collection
- Pressure waveform data

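### Edi is called consistent between modes because the catheter stays in place, but the catheter is replaced at the mode switch, so the two modes are read from two placements

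*Combined protocol and SAP*

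**What the plan says.** Section 6.2 lists "Edi (peak and min), and NAVA level" among the measures of respiratory mechanics and introduces the whole list with: "The following secondary study outcomes will be compared between NAVA and conventional mechanical ventilation treatment periods". It then says why Edi can be compared: "The NAVA catheter will be in place for the entire study (24 hour baseline and both crossover groups) for a consistent Edi measurement". Section 5.1.5 describes Edi peak and min as "measured from the Edi Catheter that will remain in place during the 11 days of data collection".

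Section 4.2 says otherwise: "Catheter will be placed prior to the baseline monitoring phase and will be replaced before going into the 2nd ventilator mode on day 7". Table 1 agrees with section 4.2. Its row "Placement of NAVA catheter" is marked in the observation phase (day 1) and again in the second mode phase (days 7-11).

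Three other parts of the plan bear on the point:
- Section 8.4.2 has catheter position confirmed by software on the ventilator.
- Section 8.1.1 intends equal allocation of the starting mode.
- Section 6.3.1 compares outcomes with a paired t-test or Wilcoxon signed rank test, and adds exploratory mixed models with subject-level random intercepts and slopes. It names no period or placement term.

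**The concern.** Edi is read from electrodes on the tube (section 1.2), so a recorded value can reflect where the tube sits as well as the child's respiratory drive. A within-child comparison is cleanest when the sensor stays the same across the two conditions. Section 6.2 claims that property, and section 4.2 removes it at exactly the point where the conditions change.

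At stake is what the Edi comparison can support. A child's NAVA minus CMV difference contains the mode effect plus whatever changed between the first and second placement, and nothing in that child's data separates the two. A reader who relies on section 6.2 would not know this, and the planned paired test does not allow for it.

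**Working it through.** **1. The passages side by side.**

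| Source | Catheter on days 1-6 | Catheter on days 7-11 |
|---|---|---|
| 5.1.5 and 6.2 | in place | stays in place |
| 4.2 and Table 1 | first placement | second placement |

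Under section 4.2, NAVA-first children have NAVA on placement 1 and CMV on placement 2. CMV-first children have the reverse. Every child who crosses over has one mode per placement. A child withdrawn before day 7 has only one placement.

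**2. What the planned analyses do about it.** The paired tests have no period term. Random intercepts and slopes do not represent a step at day 7. The sensitivity analyses that drop the first 4, 8 or 12 hours do not help, because the second placement lasts the whole of period 2.

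**3. The plan's own figures.** The only sample-size figures are for OSI (section 6.4). An exact two-sided paired t-test at alpha 0.05 and 80% power, with SD of the difference = √2 × the tabulated SD, reproduces all 24 cells (for example SD 1, difference 1: n = 18). The plan gives no figure for Edi and no placement variability.

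**4. A shift common to all second placements.** Let δ be added to every period-2 Edi value and τ be the mode effect. The NAVA minus CMV difference is τ + δ when NAVA comes second and τ − δ when it comes first. With a and b children in the two sequences and n = a + b:

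- Mean paired difference = τ + δ(a − b)/n.
- 10:10 gives 0; 11:9 gives 2/20 = 0.1δ; 12:8 gives 4/20 = 0.2δ; 13:7 gives 6/20 = 0.3δ.
- Variance of the unadjusted differences = σ² + δ² × 4ab/[n(n − 1)], where σ is their SD without the shift. At 10:10 the multiplier is 400/380 = 1.05, so the SD is inflated even when the mean is not biased. For illustration, δ = 0.5σ gives √(1 + 0.25 × 1.05) = 1.12.

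**5. What a period term does.** It estimates τ as the average of the two sequence-specific mean differences, [(τ + δ) + (τ − δ)]/2 = τ, whatever the split. It also removes the δ² component from the residual variance. Its variance is (σ²/4)(1/a + 1/b). At 13:7 this is 0.0549σ² against 0.05σ² at 10:10, a standard error √(0.0549/0.05) = 1.05 times as large. Error degrees of freedom fall from 19 to 18.

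**6. Child-specific placement error (illustration only).** With n = 20, a paired test has 80% power for a difference of 0.66 SD. Suppose each placement adds independent error with SD k times the SD of the difference. The SD then grows by √(1 + 2k²):

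| k (assumed) | SD multiplier | Detectable difference (original SD units) | Power at 0.66 SD |
|---|---|---|---|
| 0.25 | 1.06 | 0.70 | 75% |
| 0.5 | 1.22 | 0.81 | 63% |
| 1.0 | 1.73 | 1.14 | 37% |

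The values of k are assumptions. A period term does not remove this component.

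**The case against.** The strongest reply has four parts.

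- **Wording.** Section 6.2 may mean only that some catheter is always in place, so that Edi is captured under CMV as well as NAVA. That is a fair reading on availability. It does not rescue the stated purpose of consistency, and section 5.1.5 speaks of a catheter that remains.
- **Position check.** The software check in section 8.4.2 acts directly on the suspected cause and should reduce placement differences by an unknown amount. It stands as mitigation. No section requires the two placements to match or carries the check into the analysis.
- **Randomised order.** A reader might infer that the replacement biases Edi toward one mode, or that an Edi result could not be interpreted at all. The documents support neither. Replacement is tied to period, and starting mode is allocated equally. Independent placement noise enters the observed SD of the differences and widens the interval, so a null result can still be read through that interval. What remains is lost precision, plus the partial bias in step 4 if a common shift exists and completers are unequal. Some inequality is plausible: up to 25 are enrolled to obtain 20 evaluable, and equal allocation at entry does not guarantee equal completion.
- **Reach.** Edi is one of several variables within one secondary item of a pilot trial. It is not the only information on effort: section 5.1.2 records retractions and nasal flaring, and section 4.2 an asynchrony index. This limits the importance of the point but does not remove the contradiction.

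**Conclusion.** The contradiction is in the current text, and the consistency claimed in section 6.2 is a property the design does not have if section 4.2 is followed. The consequence is moderate: unquantified extra within-child noise, and a possible period effect that the paired test does not model. If second placements share a shift, the mean difference carries 0.1 to 0.3 of it with 11:9 to 13:7 completers and none with 10:10.

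A reader might want to state a percentage loss of precision for Edi. The documents give no placement variability, so any such figure, including the table in step 6, depends on the assumed input. The day-1 baseline Edi (section 3.1.2) also comes from the first placement, but section 6.3.1 names no analysis that uses it, so no conclusion is drawn there. The primary outcome is built from mean airway pressure, FiO₂ and SpO₂, not from Edi, and is unaffected.

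**What to change.** 1. Reconcile sections 5.1.5 and 6.2 with section 4.2 and Table 1, so that all four state the same thing about the catheter.
2. If the replacement stands, withdraw the claim that Edi is consistent because the catheter stays in place. State that mode and placement cannot be separated within a child.
3. Record the result of the software position check at both placements.
4. Analyse Edi with a period (placement) term, for example a mixed model with fixed effects for mode and period and a random child effect, in place of the plain paired test.

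The cost is a few sentences, one degree of freedom and a little extra recording. The period term absorbs a common placement shift together with any other period effect and cannot tell them apart. It leaves child-specific placement noise in the residual, where the confidence interval reflects it.

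Rescaling period-2 Edi by a ratio of new-catheter to old-catheter recordings on the same mode is a possible alternative, but it is not recommended. The recordings are sequential, so a real change in drive would be treated as placement error. In NAVA-first children the new catheter would itself be driving support. The ratio adds noise and may be unstable for Edi min. It would also alter the timing of a procedure.

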2.1 Primary Objective

To determine whether invasive mechanical ventilation with NAVA, as compared to CMV, improves respiratory gas exchange in prematurely born infants and young children receiving invasive respiratory support for severe BPD.

The primary study outcome is the median, time-weighted daily oxygen saturation index ([mean airway pressure x FiO₂]/SpO₂). Secondary measures of respiratory gas exchange that will be evaluated are the daily median transcutaneous pCO₂ levels (measured hourly) and the daily frequency of intermittent hypoxic events (SpO₂ < 80% for ≥ 10 seconds and less than 3 minutes) recorded by continuous SpO₂ measurement.

We hypothesize that NAVA compared with conventional mechanical ventilation will result in statistically significant reductions (p<0.05) in the median daily oxygen saturation index.

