6.3 Statistical Methods

6.3.1 Analysis Plan

Subject demographic and clinical characteristics will be summarized with standard descriptive statistics. Summarized values for the primary and secondary outcomes will be compared between the two treatment arms using paired statistical tests (Wilcoxon signed rank tests, paired t-tests) as appropriate based on the data distribution. Crossover treatment trials traditionally have a washout phase with no treatment in order to determine if all outcome measures are reflective of the current treatment and not remnants of the prior treatment. Ventilation studies are not able to have a washout phase, as it is not possible to stop providing ventilator support for a set timeframe. In addition, the timeframe needed for

a washout is unknown for change in ventilation modes. For the primary analysis, all data will be included in the analysis. As a secondary analysis we will selectively exclude the first 4, 8, and 12 hours of data to determine what washout phase may make a difference in data analysis. This timeframe will be considered a washout out phase to ensure all data collected for each mode of ventilation is related to this mode and not residual effect of the prior mode. Linear mixed effects models will be used to explore longitudinal change in the study outcomes (as continuous measures) as a function of the treatment arm. These models are well suited for repeated measurements in longitudinal studies and are capable of handling unbalanced data if present (e.g. due to drop-out). Random effects terms for both the intercept and slope will be evaluated to account for potential subject specific deviation from the cohort's overall average baseline (intercept) and change over time (slope). Model fit will be assessed using the Akaike Information Criterion.

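### Hypoxemic events are defined as a daily count with no monitored-time denominator, so the planned washout cuts, and any partial NAVA day kept in the analysis, lower the count mechanically

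*Combined protocol and SAP*

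**What the plan says.** Section 6.2, cardiorespiratory item (2), makes the outcome "The daily number of intermittent" and prolonged "hypoxemic events recorded by continuous pulse oximetry". Section 2.1 lists "the daily frequency of intermittent hypoxic events" as one of two secondary gas-exchange measures under the primary objective. Neither section, nor 6.3.1, gives monitored hours, a minimum recording time, a rule for partial days, a rate or an offset.

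Other outcomes in the plan are protected against lost hours by their form. The asynchrony index is a number of events "divided by the sum of the ventilator cycles and ineffective efforts", section 2.1 time-weights the oxygen saturation index, and mechanics and transcutaneous pCO₂ are hourly means or medians.

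Section 6.3.1 compares summarized values by paired tests without saying how daily counts are summarized over a period. The main analysis uses all data. For washout, "As a secondary analysis we will selectively exclude the first 4, 8, and 12 hours of data"; the aim is "to ensure all data collected for each mode of ventilation is related to this mode", which I read as the same cut in both modes. For trends over time, "Linear mixed effects models will be used to explore longitudinal change in the study outcomes (as continuous measures").

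NAVA can end part-way through a day. Section 5.2 stops it when a gas-exchange threshold is exceeded "for more than 2 hours from baseline while on NAVA mode", and section 8.4.2 lets the medical team return to the conventional ventilator for safety or preference.

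**The concern.** A mean, median or ratio does not fall merely because fewer hours were observed. A count does. The washout analysis asks whether early hours carry over from the previous mode, and it answers by comparing results with and without those hours. With a raw count, the result changes when hours are deleted even if there is no carry-over, so the comparison cannot be read as intended. In the longitudinal model, a shortened first day entered as a full day looks like an event rate that starts low and then rises.

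The second issue is conditional. The threshold-based exit rule is stated for NAVA only. If infants who leave NAVA contribute a partial day, that day's count covers fewer hours than the CMV days it is compared with.

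**Working it through.** **Plan's own figure.** None exists for this outcome. The only computed figures are the sample-size table in section 6.4, which concerns the oxygen saturation index. All 24 cells reproduce with a two-sided paired t-test, taking the SD of the difference as √2 times the tabulated SD (for example 18 at SD 1, difference 1). The table does not bear on this point.

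**Inputs.** Five days, or 120 h, per mode (abstract; section 3.3.1). Cuts of 4, 8 and 12 h (section 6.3.1). Planned evaluable subjects: 20 (section 3.3.2). Assumptions: a constant hourly event rate λ, and study days that start at the mode switch.

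**Washout cuts.** The expected count over h hours is λh. After a cut of w hours the first-day count is (24 − w)/24 of a full day, and the mean of five daily counts is (120 − w)/120 of its uncut value.

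| Cut | First-day count | Reduction | Five-day mean | Reduction |
|---|---|---|---|---|
| 4 h | 20/24 = 0.833 | 17% | 116/120 = 0.967 | 3.3% |
| 8 h | 16/24 = 0.667 | 33% | 112/120 = 0.933 | 6.7% |
| 12 h | 12/24 = 0.500 | 50% | 108/120 = 0.900 | 10% |

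Both modes are multiplied by the same factor. The NAVA/CMV ratio is unchanged. The absolute difference in mean daily count, 24(λ_NAVA − λ_CMV), is multiplied by (120 − w)/120, so at 12 h it shrinks by 10%.

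**Longitudinal model.** With a 12 h cut the expected daily counts within a mode are 0.5, 1, 1, 1, 1 of a full day. The least-squares slope over days 1 to 5 is [(−2)(0.5) + (−1)(1) + 0 + (1)(1) + (2)(1)]/10 = 0.10. That is an apparent rise of 10% of a full-day count per day in each mode, with a flat true rate.

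**NAVA exit, if the infant is retained.** Averaging daily counts over days with any NAVA data, at equal true rates in the two modes:

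- Exit at 12 h: 0.50 of CMV.
- Exit at 36 h: (1 + 0.5)/2 = 0.75.
- Exit at 60 h: (1 + 1 + 0.5)/3 = 0.83.
- Exit at 84 h: (3 + 0.5)/4 = 0.88.
- 12 h cut and exit at 36 h: NAVA (0.5 + 0.5)/2 = 0.50, CMV 0.90, ratio 0.56.

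The documents give no exit rate. If between 1 and 5 of 20 paired infants with similar event rates left NAVA at 36 h, the NAVA group mean would fall by 1/20 × 25% = 1.25% to 5/20 × 25% = 6.25% with no true difference.

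**Dependence on the summary.** With a median of daily counts, an exit at 60 h or later gives 1.00 and an exit at 36 h still gives 0.75. A washout cut alone also leaves the median at 1, since the median of 0.5, 1, 1, 1, 1 is 1.

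**With a denominator.** Events divided by valid hours has expectation λh/h = λ, so the NAVA/CMV ratio is 1.00 in every equal-rate case above.

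**The case against.** The strongest reply is that little follows for the mode comparison. The cuts belong to a secondary analysis and shorten both modes equally. At a constant rate the expected five-day mean of every infant shrinks by the same factor, so the sign of each paired difference, the Wilcoxon ranks and the paired t statistic are unaffected. This stands. A reader might infer from the 50% first-day loss that the washout analyses favour one mode; the documents do not support that.

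On NAVA exits, section 5.2 says such infants are withdrawn from the study, and section 3.3.2 recruits until 20 complete. An infant randomized to NAVA first who is withdrawn has no CMV period to pair. Against this, 5.2 also speaks of discontinuing the NAVA arm, 6.3.1 expects drop-out in the mixed models and includes all data in the main analysis, and no section defines an evaluable subject. Inclusion is therefore open, and the bias is conditional.

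A reader might also infer that a NAVA day cut short by deterioration would pass for a good day. That goes too far: a deteriorating infant may have a higher event rate, which would offset the lost hours, and the documents cannot show the net direction. Nor do they give any figure for oximeter signal loss or suggest that it differs by mode.

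Finally, the daily frequency in section 2.1 could be read as a rate, and no text says that a partial day is entered as a full one. But no section defines such a rate, and 6.2, taken literally, is a count.

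**Conclusion.** The point holds as a defect in the definition of one secondary outcome, with modest consequences. At a constant event rate, with study days starting at the mode switch and daily counts averaged, the washout cuts alone remove up to half of the first-day count and up to 10% of the five-day mean and of the absolute mode difference. They make the washout results non-comparable with the all-data result and put a false trend into the longitudinal model. They create no false NAVA–CMV difference.

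A between-mode bias arises only if infants who leave NAVA are retained. Its size then depends on an undocumented exit rate and an undefined summary of daily counts.

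A reader might conclude that the linear mixed model must give way to a negative-binomial one. The documents do not require it: the model is exploratory, the mode comparison rests on paired tests with a rank test available, and a count model is debatable with about 20 infants.

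**What to change.** In section 6.2 (2), define the outcome as events per 24 h of valid SpO₂ signal (24 × events / valid hours), and say what counts as valid signal. For the paired test, use total events divided by total valid hours per infant per mode, in both the all-data and the washout analyses. In the longitudinal model, use the daily rate instead of the raw count. A count model with log valid hours as offset is optional and would need a day term to serve the plan's longitudinal aim. Report valid hours by mode.

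The cost is SAP wording and one derived variable from oximetry data that are already recorded continuously and downloaded (sections 4.2 and 6.2). No procedure or sample size changes. The denominator corrects exposure time only. It does not correct for informative exit from NAVA, so the plan should separately state how infants who leave NAVA enter the analysis.

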5.1.3 Vital Signs

Vital signs for the study will be recorded from the electronic medical record and continuous multiparameter clinical monitors. Any vital signs seen outside the ranges considered clinically normal for each subject will be reported to the medical team as standard practice. All bedside care team members will be aware that the subject is enrolled in the study. BP will be monitored using the standard automated device and cuff that is being used currently. HR, Pulse oximetry, Tcom will be monitored continuously as is the standard of care for ventilated children in the N/IICU and PICU.

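### Do the overlapping duration limits for intermittent and prolonged hypoxemic events in section 6.2 need to be changed?

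*Combined protocol and SAP*

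**What the plan says.** Section 6.2 defines both classes at the same oxygen saturation threshold, below 80%.

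- **Intermittent:** at least 10 seconds and under 3 minutes. The text runs from these limits into the next class: "10 seconds and less than 3 minutes) and prolonged".
- **Prolonged:** at least the limit given in "60 seconds) hypoxemic events recorded by continuous pulse oximetry", with no upper bound.

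The use made of them is set out in the opening of 6.2: "The following secondary study outcomes will be compared between NAVA and conventional mechanical ventilation treatment periods". Section 6.3.1 adds the method: "Summarized values for the primary and secondary outcomes will be compared between the two treatment arms using paired statistical tests".

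Section 2.1 lists "the daily frequency of intermittent hypoxic events" among the gas-exchange measures, with the same 3-minute cap, and does not mention a prolonged class. Section 2.2 refers the reader to 6.2 for the list of secondary outcomes.

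On data, section 5.1.3 states "HR, Pulse oximetry, Tcom will be monitored continuously", and section 4.2 lists "Download of data from the ventilators and clinical monitoring equipment" among the procedures.

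**The concern.** Two contrasting labels suggest two separate classes, short and long. The limits do not deliver that. Nor are the classes nested, because an episode of 3 minutes or more is prolonged but not intermittent. A cap at 3 minutes seems to make sense only if longer episodes belong elsewhere, yet the other class already starts at 60 seconds.

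Three consequences would follow.

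- A difference between modes in episodes of 60 to 179 seconds shows up in both comparisons, so agreement between the two is not separate evidence.
- The sum of the two counts can exceed the number of episodes.
- If episodes moved from the 60-179 second band to beyond 3 minutes and few others crossed 60 seconds, the intermittent count would fall and the prolonged count would not rise. That could look like an improvement while hypoxemia worsened.

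**Working it through.** **1. Classification by duration (limits from 6.2).** The intermittent window is 10 to <180 s; the prolonged window is 60 s and above.

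| Duration | Intermittent | Prolonged |
|---|---|---|
| 10-59 s (band a) | yes | no |
| 60-179 s (band b) | yes | yes |
| 180 s or more (band c) | no | yes |

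The overlap is 180 - 60 = 120 s of an intermittent window of 180 - 10 = 170 s, and 120/170 = 71%. This is a share of the window's width, not of episodes. The documents give no duration distribution, so the share of episodes could be anything from 0 to 100%.

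In terms of the bands, intermittent = a + b and prolonged = b + c. Every duration of 10 s or more has a definite place in each count.

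**2. What the plan does with the counts.** Sections 6.2 and 6.3.1 compare each outcome between modes within subject. For that purpose each count must be defined identically in both periods, and it is. No section uses a + b and b + c jointly in a way that requires them to be disjoint.

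**3. The misleading pattern (an assumed day, not data).** Take six episodes of 30 s and four of 120 s, then let two of the four lengthen to 240 s. Time below 80% goes from 6×30 + 4×120 = 660 s to 6×30 + 2×120 + 2×240 = 900 s, and 900/660 = 1.36, a rise of 36%. The bands (a, b, c) go from (6, 4, 0) to (6, 2, 2).

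| Scheme | Before | After |
|---|---|---|
| As written (a+b / b+c) | 10 / 4 | 8 / 4 |
| Single cut at 60 s (a / b+c) | 6 / 4 | 6 / 4 |
| Single cut at 3 min (a+b / c) | 10 / 0 | 8 / 2 |

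The 60-second cut shows no change at all although time below 80% has risen by 36%. The 3-minute cut registers the long episodes, but its shorter class still falls from 10 to 8. That fall comes from the cap, not from the overlap. If one 30 s episode also reached 60 s, the prolonged count as written would be 5 and would show the worsening.

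**4. General lengthening (assumed exponential durations, S(t) = exp(-t/m), fixed number of onsets).** Counts per onset when the mean m goes from 60 to 90 s:

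| Scheme | Shorter class | Longer class |
|---|---|---|
| As written | S(10)-S(180): 0.797 to 0.760 (-5%) | S(60): 0.368 to 0.513 (+40%) |
| Cut at 60 s | S(10)-S(60): 0.479 to 0.381 (-20%) | S(60): 0.368 to 0.513 (+40%) |
| Cut at 3 min | S(10)-S(180): 0.797 to 0.760 (-5%) | S(180): 0.050 to 0.135 |

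The written scheme pairs the shorter class of one alternative with the longer class of the other. Its prolonged count rises with general lengthening: +95% for m from 30 to 45 s, +40% for 45 to 60 s and +40% for 60 to 90 s. Under every scheme the shorter class can fall as episodes lengthen, so the two counts have to be read together whichever is used.

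**5. What a single boundary would cost (same assumption, m = 30, 45, 60, 90 s).**

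- Cut at 60 s: the share of currently defined intermittent episodes kept is (S(10)-S(60))/(S(10)-S(180)) = 81%, 69%, 60%, 50%. It would also make 6.2 differ from 2.1, where the two now agree.
- Cut at 3 minutes: the share of currently defined prolonged episodes kept is S(180)/S(60) = 2%, 7%, 14%, 26%. That may be sparse with 20 evaluable subjects.

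**The case for a change.** The strongest case for a change is that the overlap is exact, unexplained and cheap to remove. Neither an exclusive nor a nested reading fits the text. Section 2.1 repeats the 3-minute cap, so it is not a stray figure. The counts need no new data, so only wording and an extraction rule would change. The trial is unblinded to clinicians, and two programmers might extract differently, one counting an episode twice and the other forcing it into a single class.

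Part of this stands. The overlap is real, no section says whether it is intended, and the number of distinct episodes cannot be recovered from the two counts alone. With exponential means of 30 to 90 s, (S(60)-S(180))/S(10) puts 19% to 42% of episodes of 10 s or more in both counts.

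The rest is weaker. Forcing an episode into one class needs a rule the text does not contain; applying the limits as printed is the default reading. Shared content is not peculiar to this item either: mean airway pressure and FiO2 are secondary outcomes and also components of the primary index. The plan has no composite or multiplicity scheme that needs the secondary outcomes to be distinct. Leaving the prolonged class out of 2.1 is no conflict, since 2.2 points to 6.2 for the full list.

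**Conclusion.** The overlap exists, but it does not call for a change. Followed as written, the plan gives two well-defined daily counts and a valid paired comparison of each. The pattern that could mislead is a constructed one; under the general lengthening examined above, the prolonged count rises.

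Neither single boundary is clearly better. The documents do not indicate which was intended, and each gives up something the present pair retains. That is a trade-off, and a sentence saying the overlap is intended would add detail without altering any result.

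What remains is care in reporting: the two results share episodes, should not be added, and should not be presented as independent evidence on short and long hypoxemia. Analysts can also tabulate the three bands from the same downloaded recordings, provided these hold the continuous saturation signal.

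The point is confined to one secondary outcome of a pilot trial; the primary outcome, sample size and withdrawal criteria are untouched. The classification and the 120-of-170-second figure follow from the text alone. Every percentage of episodes rests on assumed durations and serves only to compare the schemes.
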